12.3 Type of analysis

We will utilize an intent-to-treat approach to examine differences in the live birth rates for the first embryo transfer cycle in the two treatment arms in the primary analysis by the Pearson χ^2 test. Safety parameters and secondary efficacy parameters, such as pregnancy rate, miscarriage rate and other rates, will be analyzed using the Pearson χ^2 test or Fisher exact test as appropriate. Secondary efficacy parameters, including the counts and rates of oocytes/embryos, will be analyzed using the Mann-Whitney U test.

For the primary and secondary outcomes, we will also perform analysis in the per-protocol set (PPS), excluding those who have major protocol deviation(s), cancel cycle or do not complete the pre-set minimum exposure dosage of the assigned study drug (at least 80% compliance), from the ITT population. Subgroup analysis will be conducted as stratified by age (35-37, 38-39, 40-42).

Prior to unblinding, missing value in the primary outcome (live birth) and secondary outcomes (biochemical pregnancy, clinical pregnancy) in the ITT analysis will be imputed as not having an event.

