1.6 Publication committee

Members of the publication committee include [name], [name].

2. Background

The deferment of childbirth has emerged as a significant concern in recent years. Over the past forty years, the prevalence of primiparity at age of 35 years or older increased by 9 times (1). Advanced maternal age (AMA), defined as pregnancy at 35 years or older, is commonly linked with reduced fecundity (2,3). AMA patients are more inclined to the use of assisted reproductive technology (ART), including in vitro fertilization (IVF) and intracytoplasmic sperm injection (ICSI) (4). Nonetheless, their pregnancy outcomes are typically less favorable compared to their younger counterparts, as aging adversely affects both oocyte quality and ovarian reserve (5).

Traditional Chinese Medicine (TCM) has been employed for over two millennia in the treatment of a myriad of conditions, including infertility (6). A representative formula for the treatment of infertility is the Zishen Yutai Pill (ZYP). ZYP is a patent Chinese medicine invented by [name] (7). Since its market debut in 1983, ZYP was renowned for its therapeutic effects on threatened miscarriage and recurrent miscarriage. ZYP is consisted of fifteen Chinese medicine, including Cuscutae Semen, Ginseng Radix et Rhizoma, Dipsaci Radix, Taxilli Herba, Eucommiae Cortex, Morindae Officinalis Radix, Cervi Cornu Degelatinatum, Codonopsis Radix, Atractylodis Macrocephalae Rhizoma, Asini Corii Colla, Lycii Fructus, Rehmanniae Radix Praeparata, Polygoni Multiflori Radix Praeparata, Artemisiae Argyi Folium, and Amomi Fructus (8).

In previous clinical practice, the administration of ZYP was observed to enhance the ovulation and pregnancy rate, while decrease the miscarriage rate among patients with polycystic ovary syndrome (PCOS) (9). Another clinical report had suggested that oral intake of ZYP around the luteal phase could significantly increase the embryo implantation rate (10). Our previous multicenter, placebo-controlled, randomized clinical trial had suggested that the intervention of ZYP among advanced maternal aged women could significantly increase the clinical pregnancy rate during ART.

However, this analysis constituted a post hoc subgroup analysis, lacking the statistical power to detect the between-group difference. Therefore, the design of the current

study aims to provide data regarding the efficacy and safety of ZYP in IVF/ICSI for the AMA patients.

3. Objectives

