5.2 Randomization and blinding

The participants will be randomized 1:1 to receive double-blind single-dummy monotherapy with placebo or ZYP using the permuted block randomization method. The randomization will be stratified by the age (35-37, 38-39 and 40-42) by following the Human Fertilisation and Embryology Authority (11). The web-based Interactive Response Technology system is managed by independent statisticians, guiding drug dispensing.

Patients, investigators and clinical staff performing this trial will be blinded to treatment allocation. The package, appearance and odor are the same in the placebo and ZYP. The allocation and detailed information of randomization will be kept by the independent statisticians managing the Interactive Response Technology system. Blinding will be maintained until the completion of the analysis. Unblinding will be allowed in case of a medical emergency. The cause and time of unblinding will be recorded in detail and signed by the treating physicians.

When all live birth information is retrieved, the computer system will disclose the allocation.

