12.1 General statistical consideration

For continuous variables, the Kolmogorov-Smirnov test will be applied to evaluate the distribution. Variables with normal distribution will be presented as means and standard deviation (SD), and intergroup comparisons will be performed using the 2-tailed, student's t test. Variables with non-normal distribution will be presented as medians and interquartile ranges (IQR), and intergroup comparisons will be performed using the Mann-Whitney U test. Categorical variables will be summarized with frequencies and percentages and compared using chi-square test or Fisher exact test, as appropriate. All statistical analysis will be conducted with the use of the statistical package SPSS, version 19.0 (SPSS Inc). A two-sided P value of <0.05 will be considered as significantly different.

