12.2 Sample size estimation

In our previous clinical research, the live birth rate was 0.42 per embryo transfer in ZYP treated group and 0.33 per embryo transfer in placebo control group among AMA women. By assuming the same live birth rates, a sample size of 454 women in each group can provide a power of 80% at a significance level of 0.05. According to previous study, the dropout rate before ET was 15% and the cycle cancellation rate was 23% in AMA women. For this trial, a total rate of 38% (dropout and cancellation) is considered in the sample size calculation. Therefore, a total of 1466 participants

will be recruited in this study, 733 participants in each group.

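### Randomisation is stratified by age band, but the primary live-birth test ignores the bands (a small loss of power), and the age-subgroup analysis names no interaction test

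*Combined protocol and SAP*

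**What the plan says.** - **Randomisation (Section 5.2).** "The randomization will be stratified by the age (35-37, 38-39 and 40-42"). No other stratification factor is named.
- **Primary analysis (Section 12.3).** By intention to treat (ITT), the plan compares "live birth rates for the first embryo transfer cycle in the two treatment arms in the primary analysis by the Pearson" chi-square test. No stratified test or age-adjusted model is named.
- **General methods (Section 12.1).** Only unadjusted tests are listed. For binary outcomes: "Categorical variables will be summarized with frequencies and percentages and compared using chi-square test or Fisher exact test, as appropriate". The threshold is stated once for everything: "A two-sided P value of <0.05 will be considered as significantly different".
- **Subgroups (Section 12.3).** One sentence: "Subgroup analysis will be conducted as stratified by age (35-37, 38-39, 40-42"). It gives no method and no test of heterogeneity.
- **Age and the trial's rationale (Section 2).** Poorer outcomes in older women are explained "as aging adversely affects both oocyte quality and ovarian reserve". The earlier result that motivated this trial is qualified: "this analysis constituted a post hoc subgroup analysis, lacking the statistical power to detect the between-group difference".

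**The concern.** There are two separate points.

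**Primary test.** Stratifying by age makes the arms almost identical in age mix. If age predicts live birth, the treatment difference then varies less from trial to trial than an unstratified test assumes. The Pearson test uses a standard error that is slightly too large, so it rejects a little too rarely both under the null and under the alternative. This is a matter of efficiency, not validity. The design has paid for the precision and the analysis does not collect it.

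**Subgroups.** With no method given, the default in Section 12.1 would mean one chi-square or Fisher test per band at 0.05. Each band is too small for its p-value to be read alone. A significant result in one band and not in another does not show that the effect differs by age. A trial set up because an earlier subgroup finding was underpowered should say in advance how its own subgroups will be judged.

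**Working it through.** **1. The plan's own figure.** Inputs from Section 12.2: 0.42 v 0.33 per embryo transfer, two-sided 0.05, power 80%. With pooled rate 0.375:

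n = [1.96·√(2×0.375×0.625) + 0.842·√(0.42×0.58 + 0.33×0.67)]² / 0.09² = (1.342 + 0.574)² / 0.0081 ≈ 453.0, rounded up to 454 per arm.

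454/0.62 = 732.3, rounded up to 733 per arm, 1466 in total. This reproduces exactly, with an unstratified formula.

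**2. Rates per woman randomised.** Section 12.2 states that "the dropout rate before ET was 15% and the cycle cancellation rate was 23% in AMA women", which it adds to 38%. If none of these women has a live birth in the ITT analysis, the rates are 0.33×0.62 = 0.2046 and 0.42×0.62 = 0.2604. Power at 733 per arm is then about 72%.

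**3. Why the Pearson test is conservative.** Let r be the within-band binomial variance divided by the total: r = Σw·p(1−p) / [p̄(1−p̄)]. With arms balanced within bands, the true two-sided error is 2[1 − Φ(1.96/√r)].

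The documents give neither band shares nor rates by band, so both are assumed. Take shares 40/30/30% and placebo rates 48/31/15% (the strong gradient, mean 33%):
- Σw·p(1−p) = 0.4×0.2496 + 0.3×0.2139 + 0.3×0.1275 = 0.2023
- r = 0.2023/0.2211 = 0.915
- 1.96/√0.915 = 2.05, so the error is 4.0%

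**4. Pearson against age-stratified CMH.** Simulation of 400,000 trials per scenario, shares 40/30/30%, placebo rates scaled to average 33%, and a common odds ratio chosen to give 42% overall. For 733 per arm all rates are multiplied by 0.62. Entries are Pearson / CMH, in per cent.

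| Placebo rates by band | Type I error, 454 | Power, 454 | Type I error, 733 | Power, 733 |
|---|---|---|---|---|
| Flat (33/33/33) | 5.0 / 5.0 | 80.2 / 80.2 | 5.0 / 5.0 | 71.7 / 71.6 |
| Mild (40/32/24) | 4.9 / 5.1 | 80.3 / 80.6 | 4.9 / 5.0 | 71.8 / 72.1 |
| Strong (48/31/15) | 4.0 / 5.0 | 81.2 / 83.6 | 4.4 / 5.0 | 72.3 / 74.0 |
| Extreme (58/24/8) | 2.8 / 5.0 | 83.0 / 88.8 | 3.8 / 5.0 | 73.2 / 77.2 |

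A separate simulation with shares 45/25/30% gave the same picture at 454 per arm:
- rates 38/33/25.5%: 80.4 / 80.6
- rates 42/33/19.5%: 80.7 / 81.8
- rates 48/32/11.3%: 81.8 / 85.1

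**5. Subgroups, if each band is tested at 0.05.**
- Equal thirds give 733/3 ≈ 244 per arm. At 26.0% v 20.5%, power is 30.8%.
- With no effect in any band, the chance of at least one significant band is 1 − 0.95³ = 14.3%.
- With the same effect in every band, the chance that some but not all are significant is 1 − 0.308³ − 0.692³ = 0.64. Simulation with 40/30/30% shares and a common odds ratio gives 0.64 (flat), 0.65 (mild), 0.67 (strong) and 0.71 (extreme).
- Band power depends on the shares. With 293/220/220 per arm it is about 36/28/28% (flat) or 47/30/19% (strong).

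**The case against.** **The Pearson test is legitimate.** It is prespecified, matches the formula behind the sample size, and does not inflate the type I error in any scenario examined. Under a mild gradient the gain from stratifying is about 0.3 points. All of this stands, and this part would not carry much weight if the change cost anything.

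**The gradients are assumed.** This also stands. Section 2 contrasts women of 35 or older with younger women and does not say how steep the decline is between 35 and 42. The 0.62 factor further assumes that dropout and cancellation do not vary by age. The size of the loss is therefore uncertain. Its direction is not, and with no gradient the two tests agree.

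**The plan makes no claim of a differential effect.** Testing band by band is inferred from Section 12.1, and the 14% applies only if each band's p-value is read as a claim. Unlike the post hoc subgroup result of the sponsor's previous trial, these subgroups are prespecified and match the randomisation strata. That is fair, but the low power carries over, and the silence leaves the misreading open.

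**An interaction test depends on its scale.** This is correct, and the fix should name one. Under the strong gradient at 733 per arm, a common odds ratio of about 1.39 gives risk differences of about 7.3, 5.6 and 3.2 points across the bands. Tests on the two scales can disagree.

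**Conclusion.** Both parts hold. The primary test does not use the only stratification factor, and no interaction test is named for the age subgroups.

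The first part is a small matter of efficiency. About 0.3 to 2.4 points of power are lost under mild to strong gradients with 40/30/30% shares, and about 3 points under the steepest gradient examined with 45/25/30% shares. Only the extreme gradient costs about 4 points (733 per arm) to 5.8 points (454 per arm). A significant Pearson result remains valid.

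The second part has more bearing on how the results will be read. Without a rule, a mixed pattern across bands is the most likely outcome (about 64%) even when the odds ratio is the same throughout.

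The change is worth making but is not needed for validity. It does not restore 80% power: the ITT figure of about 72% comes from counting women without a transfer as having no live birth, which is a separate and larger issue.

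**What to change.** Before unblinding, amend Section 12.3 along these lines:

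- **Primary analysis.** *Live birth is compared between arms in the ITT population with the Cochran-Mantel-Haenszel test stratified by the randomisation age bands (35-37, 38-39, 40-42), two-sided 0.05. The age-adjusted risk difference is reported with its 95% CI. The unstratified Pearson chi-square test is a sensitivity analysis.* Logistic regression with age band as a covariate, or an adjusted risk ratio, would also serve; one test and one effect measure should be fixed in advance.
- **Subgroups.** *Treatment effects are given for each age band with 95% CIs, together with one treatment-by-age-band interaction test on the odds-ratio scale. Any claim that the effect differs by age rests on that test only.*

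The cost is wording. The bands are already recorded at randomisation, no new data are needed, and the sample size does not change. If age turns out not to be prognostic, the stratified test gives up about 0.1 point of power at most (71.6% v 71.7% at 733 per arm).

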The present study aims to investigate the efficacy and safety of ZYP on live birth rates among AMA infertile women during IVF/ICSI-ET. The primary objective is to determine the difference of live birth rate between the ZYP and placebo group. The secondary outcomes will include counts and rates of oocytes/embryos (oocytes retrieved, 2 pro-nuclei zygotes, cleavage zygotes, available embryos, high-quality embryos), pregnancy outcomes (rates of biochemical pregnancy, implantation, clinical pregnancy and miscarriage), incidences of maternal, fetal and neonatal complications, and neonate information (newborn birthweight and length, congenital malformation).

4. Participants

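### Safety is a stated aim, but the plan compares harms between arms only by a P value. For uncommon delivery and neonatal harms a non-significant result says little, and no interval is planned.

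*Combined protocol and SAP*

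**What the plan says.** Safety is an aim alongside efficacy. Section 2 (Background) closes by saying that the "study aims to provide data regarding the efficacy and safety of ZYP in IVF/ICSI for the AMA patients", and section 3 (Objectives) opens with: "The present study aims to investigate the efficacy and safety of ZYP on live birth rates among AMA infertile women during IVF/ICSI-ET".

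The planned comparison of harms is one sentence in section 12.3. Its subject is "Safety parameters and secondary efficacy parameters, such as pregnancy rate, miscarriage rate and other rates", and the only method it names for all of these is a Pearson chi-square or Fisher exact test. The threshold is in section 12.1: "A two-sided P value of <0.05 will be considered as significantly different". Section 12.1 also plans frequencies and percentages for categorical variables. Section 12 names no risk difference, risk ratio, confidence interval or margin for a harm, and sets out no denominator for each safety outcome.

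The sample size (section 12.2) rests on live birth alone. Section 10 and Table 6 list the safety outcomes, which are of two kinds:

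- **At or after delivery only:** postpartum haemorrhage, preterm delivery, puerperal infection, neonatal jaundice, neonatal infection, neonatal death and low birth weight.
- **Possible without a delivery:** OHSS, ectopic pregnancy and pregnancy loss. Gestational diabetes and gestational hypertension are defined by onset or recognition in pregnancy, so they are not tied to delivery either.

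**The concern.** A trial sized for live birth has far fewer women in whom a delivery or neonatal harm can occur than it randomises. If such a harm is uncommon, the likely result of a test at 0.05 is non-significance, even when the risk has doubled. A P value does not show how large an excess remains compatible with the data, and that is what a reader needs for a safety aim. Study drug continues to about five weeks after transfer in women with a positive test (section 5.4), and congenital and neonatal outcomes are among those listed, so the question is not idle.

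**Working it through.** **Inputs from section 12.2.** The plan states that "the live birth rate was 0.42 per embryo transfer in ZYP treated group" and "0.33 per embryo transfer in placebo control group among AMA women", and that "a sample size of 454 women in each group can provide a power of 80% at a significance level of 0.05". It then allows for 38% loss and randomises 733 per arm.

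**Reproducing the plan's sample size.** Take the pooled-variance formula without continuity correction, with mean rate 0.375:

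n = [1.96·√(2·0.375·0.625) + 0.842·√(0.42·0.58 + 0.33·0.67)]² / 0.09² = 453.04, rounded up to 454.

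Allowing for loss, 454 / 0.62 = 732.3, rounded up to 733. Both stated figures reproduce.

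**Women in whom a delivery harm can occur.** On placebo 454 × 0.33 = 149.8, about 150. On ZYP 454 × 0.42 = 190.7, about 191. These are live-birth deliveries under the plan's assumed effect, so stillbirths are not counted, and twins would raise the number of newborns somewhat.

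**Chance of missing a doubling.** The documents give no background rate for any harm, so the control rates below are assumptions. For each pair of event counts a (of n₁) and b (of n₂), the binomial probabilities were multiplied and summed over the pairs with P≥0.05. With t = a + b and N = n₁ + n₂, the Pearson test rejects if N·[a(n₂−b) − b(n₁−a)]² / [n₁n₂t(N−t)] > 3.84. Section 12.3 leaves the choice of test open, so the third column assumes Fisher when an expected count is below 5 and Pearson otherwise.

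150 v 191 deliveries:

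| Control → ZYP rate | Missed, Pearson | Missed, Fisher | Missed, mixed rule |
|---|---|---|---|
| 1% → 2% | 90.7% | 95.1% | 95.1% |
| 2% → 4% | 83.8% | 86.5% | 86.4% |
| 3% → 6% | 77.0% | 78.6% | 77.3% |
| 5% → 10% | 59.9% | 62.8% | 59.9% |
| 10% → 20% | 27.0% | 29.6% | 27.0% |

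Under the mixed rule, 80% power is reached for an increase from 3% to about 10.6% (roughly 3.5-fold) or from 5% to about 13.8% (roughly 2.8-fold).

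If ZYP had no effect on live birth and both arms had 150 deliveries, the range from Pearson to Fisher would be 91–98% at 1%, 84–91% at 2% and 77–85% at 3%.

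**Outcomes with larger denominators.** Chance of missing a doubling, Pearson to Fisher:

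| Control rate | 454 per arm | 733 per arm |
|---|---|---|
| 1% | 78–84% | 64–73% |
| 2% | 57–64% | 38–44% |
| 3% | 41–46% | 20–24% |
| 5% | 18–21% | 4–5% |

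**What an interval adds (assumed counts).** Take 3/150 (2.0%) on placebo and 8/191 (4.2%) on ZYP. Fisher's P is 0.36, so the planned test would return a non-significant difference. The risk difference is +2.2 percentage points, with a Newcombe 95% interval of −2.1 to +6.3. An excess of about 6 per 100 deliveries is not excluded, and the P value does not show that.

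**The case against.** Low power for rare harms is usual in a trial sized for efficacy and is not in itself an error. The plan also has more safety machinery than the test. Event frequencies and percentages will be tabulated, so a reader could derive an interval. Causality and severity are graded (13.4), serious events are reported (13.5), and a monitoring board is described (15.1). All of this stands. None of it supplies a between-arm estimate of excess risk with its uncertainty, which is the remaining gap.

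Three stronger readings are tempting, and the documents do not support them:

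- **That the plan treats P>0.05 as proof of safety.** Section 12.1 says only what counts as significantly different, and section 2 speaks of providing data on safety. No sentence equates non-significance with absence of harm.
- **That all of safety rests on 150 and 191 deliveries.** OHSS, ectopic pregnancy and general adverse events can be counted in up to 733 women per arm, where a doubling from 3% is detected about 76% to 80% of the time.
- **That the trial would find no safety difference whatever the truth.** Larger excesses, and doublings of commoner harms, would usually be found. Power is about 70% to 73% for 10% against 20%, even with 150 and 191 deliveries.

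It is also fair to say that deleting the test would be a matter of preference. Adding estimates is enough.

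**Conclusion.** The point holds as a limited one about analysis and reporting. For harms that arise only at or after delivery and occur in about 1% to 3% of controls, the planned test would miss a true doubling about 77% to 95% of the time, so a non-significant P value is not evidence of safety. The problem eases as the harm becomes commoner or the denominator larger.

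The size rests on the plan's live birth rates being met, on 454 transfers per arm, and on background harm rates that the documents do not give. What needs no assumption is that safety is a declared aim and section 12 plans no effect estimate or confidence interval for any harm. The primary result is not affected. The change is worth making because it is cheap and answers the safety aim better than the test alone.

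**What to change.** Amend section 12.3 as follows. The test may stay.

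1. For each safety outcome, state the denominator. Report counts and the risk difference with a score or exact 95% confidence interval per randomised woman and, for delivery or neonatal outcomes, also per delivery or per newborn.
2. Note beside the per-delivery figures that these groups are selected after randomisation. Per-woman figures avoid that but rise with the number of births, which the plan expects to be higher on ZYP, so both are needed.
3. For per-newborn outcomes, use an interval that allows for clustering of twins, since section 5.3.3 permits transfer of more than one embryo.
4. Base safety statements on the upper confidence limit, that is, the excess not ruled out, and state that P>0.05 does not show absence of harm.

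This takes SAP wording and standard output, with no new data, visits or participants. The downside is slightly more output and a safety statement that will read less favourably.

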6.2 Screening visit

If the patient express interest toward the clinical trial, a screening visit will be performed. Patients will be informed about the study thoroughly. During the screening visit, the following procedures will be completed.

- (1) Going through all the inclusion and exclusion criteria. Obtaining the signed informed consent form.
- (2) Collecting baseline information, including age, medical record number, and birth date.
- (3) Reviewing the medical history, including infertility history, childbearing history, gynecological surgery history, disease history and menstrual information.
- (4) Carrying out a physical examination and gynecologic examination.
- (5) Measuring the baseline sex hormones, including E₂, FSH, LH, prolactin (PRL), and testosterone (T).
- (6) Reviewing the previous ET/FET cycle record.
- (7) Dispensing information.

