6.7 Delivery visit

When the participant is preparing to deliver, the investigator will collect the delivery information and infant information according to the form designed for this visit. The delivery information mainly includes the delivery mode and pregnancy complications. The neonate information mainly includes gender, birth weight and length, birth

defects, admission to newborn intense care unit within 1 month and stillbirth.

7. Physical examination

A physical examination will be conducted on all participants by the corresponding investigator. The parameters include height, weight and they will be recorded to the nearest 0.1 cm, 0.1 kg. Height and weight will be measured without shoes, and patients will be dressed in light clothing.

8. Transvaginal ultrasound scan

An ultrasound scan with a transvaginal probe will be carried out. Uterine dimension, endometrial thickness and type, bilateral ovarian dimension, and follicle number will be measured through the ultrasound scan. The uterine size will be determined at the widest diameter. The investigator will determine endometrial types. Endometrial thickness is the largest anterior-posterior measurement of the endometrium in the sagittal plane. Ovarian dimension is measured by analysis of the largest plane of the ovary in two dimensions. In addition, antral follicle count (AFC) will be recorded.

9. Laboratory tests

Hormone and pregnancy tests will be performed at the local laboratories. In addition, blood work will be performed on screening visit, Gn initiation visit, hCG trigger day, and 2 weeks after ET. The blood sample (5 ml) will be collected with an anticoagulant tube and stored at -80°C for further analysis.

10. Outcome measures

The live birth rate is the primary outcome. The secondary outcomes will include counts and rates of oocytes/embryos (oocytes retrieved, 2 pro-nuclei zygotes, cleavage zygotes, available embryos, high-quality embryos), pregnancy outcomes (rates of biochemical pregnancy, implantation, clinical pregnancy and miscarriage),

incidences of maternal, fetal and neonatal complications, neonate information (newborn birthweight and length, congenital malformation) (14).

Live birth is defined as delivery of any viable infants after 28 weeks of gestation.

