In this study, the GnRH-a long protocol and GnRH-ant protocol will be performed according to each patient's actual situation. The GnRH-ant protocol will be used to minimize the risk of OHSS. The initial dose will be determined according to the age, basal FSH level, basal AFC, weight, and previous situation promoting ovulation. The initiation dose and total Gn dose will be adjusted according to a combined consideration of age, weight, basal hormone levels, AFC and previous cycle response. In addition, in case of high ovarian response, the cycle will be canceled to avoid OHSS. If there are three or more fetuses, then a reduction will be performed to minimize the risks of multiple pregnancies. A responsible investigator or a resident doctor on 24 h call can be contacted at each site if any adverse event occurs during this study.

Every effort will be taken to avoid injury as a result of participation. If adverse events occur, active treatment will be provided. Furthermore, if a medical dispute is involved, it will be disposed of as a routine medical event.

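### Oocyte and embryo counts are tested without the age stratum or baseline ovarian-reserve measures: a valid secondary analysis that gives up precision, by an amount the documents do not fix

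*Combined protocol and SAP*

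**What the plan says.** Section 12.3 sets the test for this family of outcomes: "Secondary efficacy parameters, including the counts and rates of oocytes/embryos, will be analyzed using the Mann-Whitney U test". Section 12.1 offers only a t test or a Mann-Whitney test for continuous variables, with the rule "A two-sided P value of <0.05 will be considered as significantly different". No adjusted or stratified test is planned for any outcome. In the analysis, age appears only as a subgroup split in 12.3.

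Elsewhere the protocol names and collects variables that bear on ovarian response:

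- Section 5.2: "The randomization will be stratified by the age (35-37, 38-39 and 40-42" years.
- Section 6.2, screening: "Measuring the baseline sex hormones", a list that includes FSH.
- Section 8: "In addition, antral follicle count (AFC) will be recorded", with no visit or date attached.
- Section 13.1, on gonadotropin dosing: "The initial dose will be determined according to the age, basal FSH level, basal AFC, weight". Section 5.3.1 names similar factors.

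**The concern.** The protocol uses age, FSH and AFC to choose the gonadotropin dose, so it treats them as informative about how a woman will respond. It then compares the outcomes nearest to that response as if nothing were known about her beforehand. Predictable variation between women stays in the error term. Ovarian reserve is not a randomisation stratum, so chance differences in it between the arms also add to the noise.

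The oocyte and embryo measures are the first-listed secondary outcomes in sections 3 and 10. They are the ones that would show whether the study drug acts before transfer. Precision lost on them makes that question harder to answer, and recovering it needs no extra participants.

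**Working it through.** **The plan's own figure.** Section 12.2 concerns live birth only: "the live birth rate was 0.42 per embryo transfer in ZYP treated group and 0.33 per embryo transfer in placebo control group", from which "a sample size of 454 women in each group can provide a power of 80% at a significance level of 0.05". With a pooled-variance two-proportion test, two-sided 0.05:

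n = [1.96·√(2·0.375·0.625) + 0.8416·√(0.42·0.58 + 0.33·0.67)]² / 0.09² = (1.342 + 0.574)² / 0.0081 ≈ 453.04, rounded up to 454 per group.

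Dividing by 1 − 0.38 gives 454/0.62 = 732.3, rounded up to 733. Both stated figures reproduce. No comparable figure exists for the oocyte or embryo counts: the documents give no SD, effect size, correlation or power for them.

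**Gain from adjustment.** Let r be the joint (multiple) within-arm correlation of the covariates with the outcome. Adjustment multiplies the residual variance by 1 − r². If the unadjusted test has power P0, then

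adjusted power = Φ( (1.96 + z(P0)) / √(1 − r²) − 1.96 ).

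Both r and P0 are assumptions. P0 = 80% is borrowed from the live-birth design.

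| r | 1 − r² | Power if P0 = 80% | Gain (points) | Power if P0 = 90% | Gain (points) |
|---|---|---|---|---|---|
| 0.2 | 0.96 | 81.6% | 1.6 | 91.1% | 1.1 |
| 0.3 | 0.91 | 83.6% | 3.6 | 92.5% | 2.5 |
| 0.4 | 0.84 | 86.4% | 6.4 | 94.3% | 4.3 |
| 0.5 | 0.75 | 89.9% | 9.9 | 96.3% | 6.3 |
| 0.6 | 0.64 | 93.8% | 13.8 | 98.2% | 8.2 |

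Worked row, r = 0.5 and P0 = 80%: (1.96 + 0.8416)/√0.75 = 3.235; 3.235 − 1.96 = 1.275; Φ(1.275) = 0.899. A 25% fall in variance is worth 1/0.75 = 1.33 times as many women. From P0 = 50% the gain at r = 0.5 is 11.9 points.

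**Check by simulation.** The formula is a normal approximation, so it was checked against the tests themselves. All inputs here are assumed.

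- 733 per arm, normal data, r = 0.5: Mann-Whitney 81.1%, rank ANCOVA 90.7%. With no effect, the rejection rates were 5.2% and 5.5%.
- 733 per arm, overdispersed counts with mean 8 and rank correlation about 0.49: 68.7% against 80.1% for a smaller effect, and 77.1% against 87.6% for a larger one.
- 560 per arm, overdispersed counts with mean 8, ratio of means 1.11, rank correlation 0.505, 1,000 replicates: Mann-Whitney 60.9%, rank ANCOVA 75.1%, proportional-odds regression 77.2%. With no effect: 3.8%, 4.8% and 5.1%.
- 560 per arm, ratio 1.11, weaker covariates, 600 replicates: gains of about 2 points at a correlation of 0.24 and 5 points at 0.34.

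The simulations show gains of the same order as the formula, and the recommended model holds its error rate near 5% even though the simulated counts do not follow proportional odds exactly.

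**Which covariates are available before dosing.** The age stratum is fixed at randomisation, and FSH is taken at screening. AFC is less certain. It is absent from the section 6.2 screening list, and section 8 gives no timing. The dated ultrasound before stimulation in section 5.3.1 is on the day of gonadotropin initiation. Under section 5.4, study drug starts earlier: on down-regulation day, or on days 19 to 23 of the previous cycle. Section 13.1 speaks of a basal AFC, so a pre-dose value may exist, but the documents do not establish it.

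**The case against.** The strongest reply is that nothing planned is wrong. In a randomised trial the Mann-Whitney test is valid without adjustment, and its 5% error rate already allows for chance imbalance in ovarian reserve. These are secondary outcomes for which the protocol claims no power. This stands in full: the point is about efficiency, not bias.

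A reader might infer that the plan loses 10 points of power. The documents do not support that as a finding. It needs r = 0.5 and a starting power of 80%, and neither is given for these outcomes. That the protocol doses on age, FSH and AFC shows they are thought relevant, not how strongly they correlate with yield. Individualised dosing could weaken the correlation. This also stands, and it is why the size is given as a range.

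A reader might also infer that baseline AFC is on record for every woman. As shown above, that is not established. Without AFC the model rests on age stratum and FSH, in women already restricted to 35 to 42 years. The documents offer no way to size that fallback.

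Finally, one correlation need not suit all the counts. Zygotes and embryos also depend on fertilisation and development, so baseline ovarian reserve may predict them less well than it predicts oocytes retrieved.

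None of this removes the point. The age stratum and screening FSH are available and cost nothing to use. The age subgroup analysis in 12.3 is not a substitute, because it splits the sample rather than adjusting the overall comparison.

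**Conclusion.** The point holds as a minor, optional improvement in efficiency. Section 12.3 leaves the randomisation stratum and collected ovarian-reserve measures out of the comparison of oocyte and embryo counts, and so gives up precision. Assuming 80% unadjusted power, the loss is about 2 to 14 points for joint within-arm correlations of 0.2 to 0.6. It is smaller where unadjusted power is already high, and possibly smaller for embryos than for oocytes. The result depends on the assumed correlation, the assumed starting power, and covariates measured before the first study dose. It does not show an invalid test or an inflated type I error, and it has no bearing on the live-birth analysis or the 1466 target.

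**What to change.** In section 12.3, before unblinding:

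- Make the main analysis of each oocyte and embryo count a prespecified proportional-odds regression on treatment, age stratum and screening FSH. This is the natural covariate-adjusted extension of Mann-Whitney. Rank ANCOVA with the same covariates is an acceptable alternative, but name one of the two.
- Add basal AFC as log(AFC+1), which is defined when AFC is zero, only where it was measured before the first study dose. Use a missing-indicator otherwise. An AFC first taken on the day of gonadotropin initiation must not be used. The sponsor should confirm from the case report form when AFC was recorded.
- Report the treatment effect with its 95% CI (an odds ratio under proportional odds).
- Keep Mann-Whitney as a sensitivity analysis for the counts and as the test for the rates.

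The cost is SAP wording, one model per count outcome and a proportional-odds assumption, which the retained Mann-Whitney test covers. No added participants or visits are needed.
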